## 4 Study Objectives

### 4.1 Hypothesis

We aim to examine the impact of cooling components of WS-3, WS-23, and menthol on the appeal and addiction potential of nicotine-containing e-liquids among adults. We hypothesize that any addition (low, high) of WS-3, WS-23, or menthol will result in similar increases in addiction potential, and that when WS-3, WS-23, and menthol are combined they will produce additive effects relative to menthol alone. We also hypothesize similar changes in appeal outcomes.

### 4.2 Primary Objective

Examine addiction potential (liking/wanting) and appeal (overall flavor appeal, intensity, sweetness, bitterness, irritation, cooling), following a single exposure (5 puffs) to nicotine-containing e-cigs (~59 mg/ml nicotine salt, commonly used in commercial e-cigs), with one of three WS-3 concentrations (none, low, high) and one of the three WS-23 concentrations (low, high, 4%) in combination with one of three menthol concentrations (none, low, high).

### 4.3 Secondary Objectives (if applicable)

Examine the interactive effects of different concentrations of WS-3, WS-23, and menthol on appeal and addiction potential.

### 4.4 Exploratory Objectives (if applicable)

An exploratory objective of this study is to examine the influence of predictors such as sex, combustible tobacco use, and nicotine dependence on study outcomes.

Another exploratory objective is to examine oral microbiome, salivary inflammatory markers and self-reported oral health status in exclusive e-cigarette users and compare the differences among users of different e-cigarette flavor groups (1. Mint/menthol, 2. fruit/sweet, 3. tobacco). We hypothesize that users of mint/menthol or fruit/sweet flavors will have higher levels of anaerobic bacteria in their oral microbiome, greater inflammatory markers in saliva, and poorer oral health compared to tobacco flavor users.

## 5 Study Design

### 5.1 General Design Description

**Pilot study:** This pilot study will establish low and high concentrations of WS-3, WS-23, and menthol concentrations to test in the main study. 30 adult e-cigarette users will participate in one laboratory session during which they will be exposed to e-liquids containing all the conditions in Table 1 without nicotine. Participants will receive a two-puff exposure to each condition; each exposure will be separated by 10 mins to allow the flavor to dissipate, similar to our prior work on menthol. Each session will begin with familiarization with the sensory rating scales used in the current study and training in how to puff the lab e-cig in a directed and standardized way. WS-3, WS-23 and menthol will be presented in blocks (block order will be counterbalanced) with each block presenting increasing menthol/WS-3/WS-23 concentrations as in our earlier work. Participants will rate “coolness” using the generalized Labeled Magnitude Scale (gLMS), an established category ratio scale with 7 semantic labels: “no sensation”, “barely detectable”, “weak”, “moderate”, “strong”, “very strong”, and “strongest imaginable sensation of any kind”, positioned quasi-logarithmically based on their semantic magnitude. Using averages of participant ratings, we will select a low concentration of each constituent that is rated as more than “barely detectable” but less than “moderate” to ensure that cooling is weak but clearly perceptible. For the high concentration of each constituent, we will select a concentration that on average falls between “strong” and “very strong” to identify a strong cooling sensation while avoiding sensations that would also be uncomfortable. We will also determine *overall flavor intensity, sweetness, and harshness/irritation* using the gLMS. During the lab sessions, we may have participants wear a small smartband on their wrist, on the same hand they use to vape the e-cigarette. The smartband collects movement data from geospatial sensors as the participant moves their arm and hand. The sensor data will be used to measure the movement during the directed e-cigarette puffing during the lab session. The smartband is only being used for data collection and is not being evaluated/used as a medical device. There are no changes to the lab procedure or puffing instructions.

**Table 1.** Pilot Study Design

	Concentration 1	Concentration 2	Concentration 3	Concentration 4	Concentration 5	Concentration 6
WS-3 Block	0.05%	0.1%	0.5%	1.0 %	2.0 %	-
WS-23 Block	0.05%	0.1%	0.5%	1.0 %	2.0 %	4.0%
Menthol Block	0.05%	0.1%	0.5%	1.0 %	2.0 %	-

**Table 2.** Main Study Experimental Design

	No WS-3	Low (0.1%) WS-3 Concentration	High (2.0%) WS-3 Concentration	Low (0.1%) WS-23 Concentration	High (2.0%) WS-23 Concentration	4% WS-23 Concentration
Low (0.1%) Menthol	S 1 -S 66					
High (2.0%) Menthol	S 1 -S 66					
No Menthol	S 1 -S 66					

S=Subject. All subjects (1-66) will be exposed to all conditions in the adjacent table.

**Main Study:** The purpose of the main study will be to determine sensory responses following exposure to e-liquids containing nicotine and WS-3, WS-23, and menthol. This study will recruit 66 adult e-cigarette users (50% with current cigarette use, of which 50% will use menthol cigarettes), to participate in 3 laboratory sessions, separated by at least 24 hrs. At the intake visit, participation in the oral microbiome and inflammatory marker testing will be optional for exclusive e-cigarette users (up to 33). Specifically, they will be asked to provide saliva and urine samples for oral microbiome and inflammatory marker testing and complete a brief survey about their oral health status. Additionally, participants will be asked to submit their most used e-cigarette device/pods from the past-month for analysis. These will be used as exploratory assessments. During the lab visits, participants will receive all eighteen conditions shown in Table 2 below and will be asked to abstain from tobacco use for two hours prior to session start (to control for time since last tobacco exposure). Participants will be randomized to receive one of the 3 menthol conditions (no-menthol, low menthol, high menthol, levels determined by the pilot study above) in Lab 1 and will receive the alternative conditions in randomized order in Lab 2 and Lab 3. During each lab session the menthol condition will be paired with three WS-3 concentrations: no WS-3, low (0.1%) WS-3, or high (2.0%) WS-3 and three WS-23 concentrations: low (0.1%) WS-23, high (2.0%) WS-23, or 4% WS-23 (concentration determined by pilot study) in randomized order. All e-cigarettes will contain nicotine salt at a nicotine concentration of ~59mg/ml, commensurate with levels in popular commercially available nicotine salt e-cigarettes. Each exposure will consist of a 5-puff bout (each puff 3-sec long and separated by 30 sec.) collected via a puff topography device (an apparatus used to measure puffing behavior) and will be separated by 30 mins to allow any sensory effects to dissipate between exposures. To precisely measure puffing behavior, we will utilize a validated electronic cigarette topography device (eTop). This device connects to a computer with software designed to measure puffing behavior. An e-cigarette is inserted into a silicone mouthpiece and the mouthpiece is connected to tubing which feeds into the device. As a participant inhales this device measure puffing behavior including number of puffs, puff volume, puff duration, puff flow rate (a calculation of volume/time). These indices help us understand vaping behavior and make it possible to compare e-cigarette exposure across participants. Topography mouthpieces are sanitized in between subjects and inhaling e-cigarettes via topography devices present no increased risk to participants. At the end of each of the three lab sessions, participants will choose between the 6 e-liquids they sampled in the lab using a free-choice paradigm (~30 mins).

Each session will begin with administration of baseline questionnaires assessing withdrawal and craving, collection of samples to assess nicotine levels, familiarization with the sensory and hedonic rating scales and training in how to puff the lab e-cig. Training will be conducted using e-cigs that contain the base liquid of 50% propylene glycol (PG)/50% vegetable glycerin (VG) with no nicotine. Similar to our earlier trials, after each exposure, participants will rate addiction potential (*liking/wanting*: Drug Effects Questionnaire (DEQ); and appeal (*overall flavor appeal*: Labeled Hedonic Scale (LHS); *flavor intensity*: overall flavor intensity, irritation, coolness, sweetness, bitterness: generalized Labeled Magnitude Scale (gLMS). Salivary nicotine samples will be collected pre-sessions and after each flavor exposure to assess potential impact of nicotine levels on responses, with participants

rinsing their mouths before providing each sample. A brief description of the e-cigarette device and all ingredients that will be used for the pilot and main studies is included in Table 3.

**Table 3.** Description of all investigational tobacco products.

Ingredients or products	Manufacturer name	Concentrations (mg/ml or %)
E-cigarette device	Suorin iShare™	-
PG	JT Baker: Propylene Glycol, U.S.P. - F.C.C.	50%
GL	Fisher Scientific: Glycerol, USP/FCC	50%
Nicotine Salt	Nicotine River: PurNic Smooth Nicotine Salt 100mg/ml in 50PG/50GL	0 or 59mg/ml
Menthol	Sigma-Aldrich: L-Menthol	0.05%, 0.1%, 0.5%, 1.0%, and 2.0%
WS-3	Sigma-Aldrich: WS-3	0.05%, 0.1%, 0.5%, 1.0%, and 2.0%
WS-23	Vigon: 503872	0.05%, 0.1%, 0.5%, 1.0%, 2.0%, and 4.0%

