### **5.2.2 Secondary Outcome Variables (if applicable)**

E-Cigarette Craving: The Yale Craving Scale

Salivary Nicotine/Cotinine Levels

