### **6.4 Statistical Method**

#### **6.4.1 Statistical Design**

Preliminary analyses will provide an overview of the data (e.g., randomization success, outcome distribution, missingness patterns). Outcome analyses will be intent-to-treat and use mixed-effects models which allow for different numbers of observations/subject, use all available data, and can handle missing-at-random data. If model assumptions will appear to be violated, we will transform the data or fit more flexible generalized linear or nonparametric mixed models. For the pilot study, separate mixed-effects models will examine the influence of different concentrations of menthol, WS-23 and WS-3 on coolness and overall intensity and will be used to select the concentrations of menthol and WS-3 that product the weak but detectable coolness and the maximum coolness. For the main study, separate mixed-effects model will include menthol (0, Concentration 1, Concentration 2), WS-3 (0, Concentration 1, Concentration 2), WS-23 (0, Concentration 1, Concentration 2, Concentration 3) and time within lab as factors, all interactions among those factors and adjust for stratification variables. A combination of random effects and structured variance-covariance matrices will be used to account for within-subject correlations. The best-fitting structure will be selected based on Akaike information criterion (AIC). For the main study, higher liking/wanting for WS-3 (at Concentration 1 or 2) or WS-23 (at Concentration 1 or 2 or 3) combined with menthol (at Concentration 1 or 2), compared to menthol alone, will be supportive of the primary hypothesis. Similar models will examine the other outcomes and interactions of different concentration combinations of WS-3, WS-23 and menthol with nicotine. Exploratory analyses will also consider the impact of sex, combustible tobacco use and nicotine dependence on experiences from WS-3, menthol and nicotine.

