#### **6.5.7 Subsets and Covariates**

As noted, we will stratify by menthol cigarette status in randomization and include as a covariate in analyses as that is a known confound to ratings of cooling e-cigs. If necessary, we will also adjust for participant abstinence compliance.

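### Session-start craving, withdrawal and salivary nicotine are collected but left out of the models, so contrasts between menthol levels give up some precision

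*Combined protocol and SAP*

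**What the plan says.** Section 5.1 (Main Study) schedules the session-start measurements: "Each session will begin with administration of baseline questionnaires assessing withdrawal and craving, collection of samples to assess nicotine levels". It also gives the purpose of the saliva samples: "Salivary nicotine samples will be collected pre-sessions and after each flavor exposure to assess potential impact of nicotine levels on responses". Table 4 places saliva, the Drug Effects Questionnaire (which has a withdrawal subscale, 6.2.1) and a craving questionnaire at Labs 1 to 3.

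The analysis sections do not take these values up. The main-study model, stated in 6.4.1 and again in 6.5.1, contains menthol, WS-3, WS-23 and "time within lab as factors, all interactions among those factors and adjust for stratification variables". Section 6.5.7 names one covariate, "we will stratify by menthol cigarette status in randomization and include as a covariate in analyses", and then adds "If necessary, we will also adjust for participant abstinence compliance". It gives no criterion for necessity and no definition of compliance. Craving ("E-Cigarette Craving: The Yale Craving Scale") and salivary nicotine/cotinine appear in 5.2.2 only as secondary outcomes.

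On design, 5.1 says "Participants will be randomized to receive one of the 3 menthol conditions" in Lab 1, with the other two levels in Labs 2 and 3. All six coolant conditions are given inside each session at that session's menthol level. The hypothesis in 4.1 is that "any addition (low, high) of WS-3, WS-23, or menthol will result in similar increases in addiction potential".

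**The concern.** Menthol is a between-session factor and coolant a within-session factor. The similar-increases hypothesis in 4.1 needs menthol alone against no menthol, and WS-3 or WS-23 alone against menthol alone. Each of these compares ratings from different days. Day-to-day variation in craving, withdrawal and recent nicotine intake adds noise to them, and also to the menthol contrasts for craving and salivary nicotine themselves. The only named covariate, menthol cigarette status, is fixed within a person and cannot reduce that noise.

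Three things are at stake:
- Precision on the cross-session contrasts. This matters for a claim of similarity, because a noisy comparison can pass for similarity.
- A stated purpose of the saliva samples that no analysis section turns into a model term.
- A choice of model for abstinence that can be made after the ratings have been seen.

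**Working it through.** 1. The plan's own figure. From 6.4.2: 60 completers, SD of paired differences 25, difference 11.4, alpha 0.01, paired t-test. Noncentrality = (11.4/25) × √60 = 0.456 × 7.746 = 3.53 on 59 degrees of freedom. Two-sided power is 80.4% and the detectable difference is 11.35. Sidedness is not stated, but two-sided reproduces the plan's 80%.

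2. Which contrasts a session baseline can affect. Write a rating as subject effect + session effect (variance τ²) + residual (variance σ²).
- Two products in the same session: the session effect cancels and the variance of the difference is 2σ². The four contrasts in 6.4.2 are of this kind. An SD of 25 gives σ² = 625/2 = 312.5 and SE = 25/√60 = 3.23. No session-level covariate changes this.
- One product in each of two sessions (for example menthol alone versus none): the variance is 2(τ² + σ²).
- Two sessions, each averaged over its six products: the variance is 2(τ² + σ²/6).

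3. Gain from adjustment. A session-level covariate with correlation r to the session effect removes r²τ². The proportional fall in the SE is 1 − √(1 − s·r²), where s is the session share of the variance: τ²/(τ² + σ²) for a single cell and τ²/(τ² + σ²/6) for the six-product average.

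4. Inputs the documents do not give. Assumed: r = 0.3 to 0.5 and τ² = 50 to 312.5. With σ² = 312.5:
- single cell: s = 50/362.5 = 0.138 up to 312.5/625 = 0.50
- six-product average (σ²/6 = 52.1): s = 50/102.1 = 0.490 up to 312.5/364.6 = 0.857

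| Contrast | s | r = 0.3 | r = 0.5 |
|---|---|---|---|
| Single cell | 0.138 | 0.6% | 1.7% |
| Single cell | 0.50 | 2.3% | 6.5% |
| Average of six | 0.490 | 2.2% | 6.3% |
| Average of six | 0.857 | 3.9% | 11.4% |
| Upper limit, all variance session-level | 1 | 4.6% | 13.4% |

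At r = 0 every entry is zero.

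5. Simulation check (60 subjects, 3 sessions, 6 products, the same variances). For the six-product average, adjustment cut the SE by about 2–4% at r = 0.3 and 5–12% at r = 0.5. For single cells the cuts were about 0.5–2% and 1–7%. There was no gain at r = 0. The SE of the within-session contrast stayed near 3.2 in every setting.

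**The case against.** The strongest reply is that the primary inference is untouched. Sections 6.4.1 and 6.5.1 judge the primary hypothesis by coolant plus menthol against menthol alone, and 6.4.2 powers four such contrasts, all within a session. This stands. A reader might infer that the 80% power is compromised. It is not, and interactions built from within-session differences are equally unaffected.

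A reader might also infer that the menthol contrasts are biased. Menthol order is randomised, so leaving the baselines out costs precision only. Nor do all analyses of the two secondary outcomes lose precision: their coolant contrasts are within-session too, and only their menthol contrasts can gain.

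The plan already does something about recent exposure. It requires two hours' abstinence and models within-subject correlation. That limits the noise but does not use the measured values. The abstinence rule and the stated purpose of the saliva samples suggest that the investigators themselves expect recent nicotine to bear on the ratings.

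There are also fair cautions about adjustment:
- Raw session baselines mix differences between people with differences within a person.
- Lab 2 and Lab 3 baselines follow earlier exposures, at least 24 hours before, so they are not strictly pre-treatment.
- A missing baseline would drop all six ratings of that session from a standard mixed model, against the aim in 6.5.8 of using all available data.
- Pre-session salivary nicotine also reflects usual intake, so it does not measure abstinence compliance cleanly.

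These bear on how the covariates are specified. The first and third can be met in the specification, and none removes the case for using a baseline already collected.

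**Conclusion.** The point holds as a modest efficiency and pre-specification gap, confined to contrasts that cross sessions. Under the assumed r of 0.3 to 0.5 and a session share of 14% to 50% of single-observation variance, adjustment would cut the SE by about 0.6% to 6.5% for single-cell contrasts such as menthol alone versus none, and by about 2% to 11% for menthol contrasts averaged over six products. It is tempting to quote 5% to 13% for all of these. That range requires all the variance to be session-level, so it is an upper bound; nothing in the documents supports it as the expected gain. With no within-person correlation there is no gain.

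The case is clearest for craving and salivary nicotine, where the matching baseline is the natural covariate. The open-ended abstinence adjustment needs settling whatever the correlation turns out to be.

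**What to change.** In 6.4.1 and 6.5.1:
- For craving and salivary nicotine, pre-specify the matching session-start value as a covariate. State which craving scale is used at session start, since 5.1 does not name it.
- For the other outcomes, include session-start craving, withdrawal and salivary nicotine when estimating cross-session menthol contrasts.
- Use pre-exposure values only, because samples taken after exposure are affected by the product. Enter each covariate as a subject mean plus a within-subject deviation.
- State a rule for a missing baseline, such as imputation, so that the session's ratings are kept.

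In 6.5.7, replace the conditional abstinence adjustment with one fixed before the data are seen. Define compliance separately, and do not treat salivary nicotine as equivalent to it.

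The cost is SAP wording, a few degrees of freedom against about 180 sessions (60 × 3), and the work of handling missing baselines. No new data are needed, and the sample size and primary contrasts stay as they are.

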### 5.1.1 Study Date Range and Duration

The expected duration of this study is 09/2023 – 09/2026 (3 years). The expected duration/participant is 3 weeks to complete the intake and single laboratory session for the pilot study and 5 weeks to complete the intake + 3 laboratory sessions for the main study. Recruitment and enrollment for the main study will start after the completion of the pilot study (tentatively by the end of year 2024), meaning after all 30 pilot subjects have completed their lab sessions and the arm is closed.

### 5.1.2 Number of Study Sites

The study will take place at the Yale University School of Medicine. Study sites will include the Connecticut Mental Health Center (CMHC; [name]) or the Substance Abuse Treatment Unit (SATU; [name]) for intake appointments and Pierce Laboratories ([name]) or West Campus Research Unit (WCRU; [name]), which are equipped with ventilated research chambers utilized for smoking and vaping research studies.

## 5.2 Outcome Variables

The outcome variables in this study are appeal, sensory effects, and reinforcing value (detailed below).

### 5.2.1 Primary Outcome Variables

Liking/Wanting: Drug Effects Questionnaire

Labeled Hedonic Scale (LHS): Flavor/Sensory Perception

Generalized Labeled Magnitude Scale (gLMS): Ratings of Flavor Intensity, Sweetness, Coolness, Irritation/Harshness, Bitterness

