# Synopsis

## Primary Objective

The primary objective of this study is to examine the appeal and addiction potential of e-cigs containing WS-3, WS-23 (synthetic coolants), with and without menthol, and nicotine. A pilot study will determine appropriate concentrations of WS-3, WS-23, and menthol.

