## Primary Outcome Variables

Liking/Wanting: Drug Effects Questionnaire

Labeled Hedonic Scale (LHS): Flavor/Sensory Perception

Generalized Labeled Magnitude Scale (gLMS): Ratings of Flavor Intensity, Sweetness, Coolness, Irritation/Harshness, Bitterness

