#### **6.4.2 Sample Size Considerations**

For our pilot study, we will recruit 30 subjects. While we did not conduct a power calculation for this pilot study, we conducted a similar pilot study with 10 participants in our earlier work with multiple menthol concentrations, and do not anticipate any problems with identifying differences in coolness between the WS-3 and menthol concentrations. For the main study, we will recruit 66 subjects. With an anticipated dropout of 10%, 60 subjects are expected to have complete data. Because we have 4 primary hypotheses (each WS-3 concentration X each menthol concentration > menthol concentration alone), we used a Bonferroni-corrected alpha=0.1. With N=60 completers and a SD of paired differences of 25 as observed in our prior data, we have 80% power to detect a difference of 11.4 (moderate effect size  $d'=.45$ ) in liking/wanting (0-100 scale) between each WS-3 concentration X each menthol concentration and menthol alone using a paired t-test at alpha=0.01.

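### Section 6.4.2 corrects for 4 WS-3 hypotheses at an alpha given as both 0.1 and 0.01, but the support rule has 10 liking/wanting contrasts; six of the seven primary ratings have no rule

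*Combined protocol and SAP*

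**What the plan says.** **Support rule.** Section 6.4.1 takes as support for the primary hypothesis "higher liking/wanting for WS-3 (at Concentration 1 or 2) or WS-23 (at Concentration 1 or 2 or 3) combined with menthol" at either non-zero menthol level, against menthol alone. Section 6.5.1 repeats the rule. Both leave the remaining outcomes to similar models, and neither states an alpha.

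**Sample size.** Section 6.4.2 says "we have 4 primary hypotheses (each WS-3 concentration X each menthol concentration > menthol concentration alone", a definition with no WS-23 condition in it. On that count, "we used a Bonferroni-corrected alpha=0.1". The power sentence that follows uses 0.01 instead: 80% power for a difference of 11.4 on the 0-100 scale, with 60 completers, an SD of paired differences of 25 and a paired t-test. Sidedness is not given.

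**Place of WS-23.** The Synopsis sets the primary objective as to "examine the appeal and addiction potential of e-cigs containing WS-3, WS-23 (synthetic coolants), with and without menthol, and nicotine". Sections 4.1 and 4.2 also name WS-23.

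**Outcomes.** The Synopsis and 5.2.1 list as primary the DEQ liking/wanting score, "Labeled Hedonic Scale (LHS): Flavor/Sensory Perception" and "Generalized Labeled Magnitude Scale (gLMS): Ratings of Flavor Intensity, Sweetness, Coolness, Irritation/Harshness, Bitterness". No order or hierarchy is given. The primary objective in 4.2 has the same scope: "Examine addiction potential (liking/wanting) and appeal (overall flavor appeal, intensity, sweetness, bitterness, irritation, cooling". Section 4.1 adds: "We also hypothesize similar changes in appeal outcomes".

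**The concern.** Section 6.4.2 does not describe the rule that 6.4.1 and 6.5.1 apply. Six of the ten contrasts that can support the primary hypothesis involve WS-23, and none of the six is in the count behind the correction. The per-test alpha appears with two values a factor of ten apart in the same paragraph. A reader of the results would not know at what level a WS-23 finding on liking/wanting was meant to be tested.

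The outcome labels raise a related question. Seven ratings are called primary, but only one has a support rule and a power calculation. For the other six, no alpha, decision rule or adjustment is given, so the plan does not say whether a significant LHS or gLMS result is a primary finding.

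**Working it through.** **1. Counts.** The inputs come from 5.2.1, 6.4.1, 6.4.2 and 6.5.1.
- Primary ratings: 1 (DEQ liking/wanting) + 1 (LHS) + 5 (gLMS) = 7.
- Contrasts in the support rule: 2 WS-3 levels × 2 menthol levels + 3 WS-23 levels × 2 menthol levels = 4 + 6 = 10.
- Hypotheses in 6.4.2: 2 WS-3 levels × 2 menthol levels = 4.

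**2. The plan's own power figure.** The check is a paired t-test with n = 60, SD = 25, difference 11.4, using the noncentral t with 59 degrees of freedom. The standardised difference is 11.4/25 = 0.456 (the plan says .45), and the noncentrality is 0.456 × √60 = 3.53.

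| Per-contrast alpha | Power at 11.4 points | Difference with 80% power |
|---|---|---|
| two-sided 0.1 | 96.8% | 8.1 |
| one-sided 0.01 | 87.0% | 10.5 |
| two-sided 0.0125 (= 0.05/4) | 82.7% | 11.1 |
| two-sided 0.01 (same upper cutoff as one-sided 0.005) | 80.4% | 11.35 |
| two-sided 0.005 | 72.8% | 12.2 |

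Only the two-sided 0.01 cutoff returns the stated 80% for 11.4. The calculation was evidently run at that cutoff, and 0.1 does not fit it. Neither printed alpha equals 0.05/4 = 0.0125.

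**3. Familywise error at that cutoff.** The Bonferroni bounds are:
- higher ratings only: 10 × 0.005 = 0.05 over all ten contrasts, and 4 × 0.005 = 0.02 over the four WS-3 contrasts;
- either direction: 10 × 0.01 = 0.10, and 4 × 0.01 = 0.04.

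Contrasts at one menthol level share a menthol-alone cell, so the bounds are somewhat conservative. A simulation of 40,000 null trials (n = 60, one outcome, two menthol-alone cells each shared by five contrasts, independent equal-variance cells, paired t, any one significant contrast counted) gave:

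| Family | Higher only | Either direction |
|---|---|---|
| 10 contrasts | 4.2% | 8.4% |
| 4 WS-3 contrasts | 1.9% | 3.8% |
| 6 WS-23 contrasts | 2.7% | 5.4% |

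If 0.01 had been meant one-sided, false support would be 8.1% over ten contrasts and 3.7% over four.

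**4. What a correction for ten would need.** The plan states no family level, so 5% is an assumption here. Then 0.05/10 = 0.005 per contrast.
- One-sided 0.005 is the cutoff already used for power: 80.4% at 11.4 points, with nothing to restate.
- Two-sided 0.005 gives simulated error of 4.3% in either direction over ten contrasts. Power at 11.4 points is 72.8%, and 80% power is reached at 12.2.

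**The case against.** The best defence is that the plan's direction already protects it. The rule counts only higher liking/wanting, and the hypotheses in 6.4.2 are written as greater-than. The cutoff that reproduces the power figure is 0.005 in that direction, exactly 0.05/10. On that reading false support is bounded at 5% over all ten contrasts, WS-23 included. This stands. A reader might infer from the mismatch of 4 and 10 that error control is already lost; the documents do not support that.

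Nor does it follow that the WS-23 contrasts are underpowered. Every subject receives all 18 conditions, and the power is per contrast. With the same n, SD and cutoff, a WS-23 contrast also has 80.4%. The omission is in the wording; no numerical shortfall is shown unless the WS-23 SD differs.

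Two further points stand in part. The 0.1 is most likely a slip, but correcting it would leave WS-23 out of the count and sidedness unstated. Sections 6.4.1 and 6.5.1 call the results supportive and do not say that one significant contrast is enough; the planned analysis is also a factorial mixed model. Treating any one of ten paired tests as success is therefore an assumption of the error figures.

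On the outcomes, it is tempting to conclude that the six appeal ratings must be demoted. The documents do not force this: the Synopsis, 4.1 and 4.2 put appeal in the primary objective and hypothesis. The defect is the missing hierarchy or multiplicity rule, which can be supplied in more than one way.

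**Conclusion.** Section 6.4.2 is wrong as written against 6.4.1 and 6.5.1: it counts 4 hypotheses where the rule has 10, leaves out WS-23, and states alpha as both 0.1 and 0.01. It would be too strong to say that error and power cannot be recovered from the plan. The cutoff can be inferred from the 80% figure; what is missing is the intended sidedness and family level.

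At that cutoff, familywise error over the ten contrasts is about 4% counting only higher ratings and about 8% in either direction. No inflation is shown if a one-sided 5% family is meant; it is shown if a two-sided 5% family is meant. These figures assume 60 completers, SD 25, independent equal-variance cells, paired t-tests and any single significant contrast counting as support. They concern liking/wanting alone.

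The seven primary labels are a separate gap in the same plan: six ratings carry the label with no stated rule. Both are worth correcting before analysis, and neither undermines the design.

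**What to change.** **Hypotheses and alpha.** In 6.4.2, replace the 4 hypotheses with the 10 in the support rule, correct the 0.1, and state sidedness and family level. Repeat the alpha in 6.4.1 and 6.5.1. Then:
- *One-sided 5% family:* 0.005 per contrast; the power statement stands (80.4% for 11.4 points). The cost is that a lower rating cannot be a primary finding.
- *Two-sided 5% family:* 0.005 per contrast, or Holm, or a Dunnett-type adjustment for the shared comparator. Restate power under Bonferroni as about 73% for 11.4 points, or 80% for 12.2. The cost is the lower stated power; no increase in enrolment is proposed.

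**Outcomes.** State that DEQ liking/wanting is the confirmatory outcome. Then either move the LHS and gLMS ratings to secondary, aligning the Synopsis, 4.1, 4.2 and 5.2.1, or keep their label and give them a stated multiplicity rule (Holm or false discovery rate). The first choice makes appeal secondary although the objective names it; the second keeps the objective intact.

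**Record.** Main-study recruitment was to follow the pilot, tentatively finished by the end of 2024 (5.1.1), and the latest revision is dated 8/01/25, so enrolment may have begun. Record the date of the change, how many main-study participants were enrolled by then, and whether any outcome data by condition had been seen.

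The change is text only, through an approved modification under 7.13, with no new data and no added participants.
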